#### ***E. Exclusion Criteria***

The participant must not exhibit any of the following:

1. Requires fusion at more than two segments.
2. Has had previous fusion surgery at the segment(s) to be treated (previous discectomy, laminotomy, laminectomy or nucleolysis at the segment(s) to be treated  $\geq$  6 months ago is ok).
3. Has  $> 11^\circ$  lumbar scoliosis.
4. Has  $> 40$  BMI.
5. Has  $>$  Grade 1 spondylolisthesis.
6. Smokes (see previous page).
7. Has osteoporosis, osteomalacia, Paget's disease or metabolic bone disease.

Osteoporosis should be assessed at the time of the pre-operative evaluation based on the participant's history, physical examination and review of the radiographic evaluations (i.e., DXA scan). According to the World Health Organization (WHO):

- A T-score of -1.0 or above is normal bone density (e.g., 0 and -0.9).
- A T-score between -1.0 and -2.5 is low bone density or osteopenia (e.g., -1.1 and -2.4).
- A T-score of -2.5 or below (e.g., -2.6 and -3.9) is osteoporosis. These patients must be excluded.

8. Has a disease that significantly inhibits bone healing (e.g., uncontrolled diabetes type 1, renal failure, impaired calcium metabolism).
9. Has a medical condition that requires or has a history of chronic steroid use (i.e., oral steroids), with the exception of inhaled/nasal corticosteroids steroids or has any medical condition that requires treatment with drugs known to interfere with bone healing.
10. Has a neurological disease (e.g., Parkinson's disease), a psychosocial disorder (e.g., suicidal, diminished capacity) or has a history of substance abuse which would preclude accurate evaluation or limit the ability to comply with study requirements.
11. Has either an active infection or infection at the site of surgery
12. Has a systemic disease (e.g., AIDS, HIV, active hepatitis, tuberculosis)
13. Has rheumatoid arthritis or other autoimmune disease.
14. Has spinal tumors.
15. Has an active malignancy (except non-melanoma skin cancer) or history of any invasive malignancy unless treated and in remission for at least five years.
16. Has a known sensitivity or allergies to porcine collagen, PEEK, tantalum or titanium.
17. Has active arachnoiditis.
18. Has fractures of the epiphyseal plate or fractures for which stabilization of the fracture is not possible.
19. Is a prisoner.
20. Is involved in spinal litigation at the treated segment(s) (workers compensation cases may be included if uncontested).
21. Is participating in another clinical study that would confound Study data.
22. Is pregnant or is interested in becoming pregnant while participating in the Study.

If any of the following criteria are met during the surgery, a participant may be excluded:

- Unilateral instrumentation was used.
- A lateral or anterior technique/device was used to complete the procedure.
- A synthetic bone void filler was used in and/or around the IBF device.
- A non-PEEK IBF device was used to complete the procedure.
- Less than 2.5 cc of autograft bone was used on each side of the posterolateral spine at each treated segment.
- BMA was not used to rehydrate nanOss Bioactive 3D.
- Bone graft material other than autograft bone, autologous BMA and nanOss Bioactive 3D was used in the posterolateral spine.

#### ***F. Participant Disposition or Lost to Follow-Up***

It is expected that participants will complete the Study, and the PI will make every attempt to contact the participant to have the participant continue in the Study. If the participant is lost to follow up despite all attempts, the PI (or designee) will complete and sign the appropriate CRF.

The following are circumstances for which a participant would be identified as not continuing his or her participation in the Study:

- Lost to follow-up and no additional data is available on the participant's outcome.
- Participant died.

All information regarding the participant discontinuation in the Study will be recorded and includes:

- When the participant completes the Study.
- Indicates how the participant left the Study at their final visit.

For participants that are lost to follow-up, data from the visits that were completed will be used.

#### ***G. Withdrawal criteria***

Participants will be advised that they may voluntarily withdraw from the Study at any time and will be instructed to notify the PI immediately. Participants may choose to withdraw for any reason and will be asked to reveal their reasons for withdrawal to the Sponsor.

A participant may be withdrawn from the Study without consent by the PI for any of the following reasons:

- The participant may relocate to another geographical area, which requires a change of the physician.
- The participant may be unable to continue participation in the Study due to some significant though unrelated condition or accident.
- The participant may be withdrawn from the Study by the PI or the Sponsor for noncompliance with the Study procedures.

All information regarding the participant discontinuation in the Study will be recorded and includes:

- When the participant completes the Study.
- Indicates how the participant left the Study at their final visit.

For participants that withdraw or are withdrawn, data from the visits that were completed will be used.

#### ***H. Duration of Participant Participation***

The expected duration of participant participation is approximately 24 months.

### ***I. Completion of the Study***

When the last participant enrolled completes the Study, and the information has been recorded on the appropriate CRF, the Study will be considered as completed.

## XIII. METHODS

### ***A. Schedule of Events***

Pre-operative, operative, discharge and post-operative follow-up data will be collected on all participants. The complete list of events is a supplemental document. A summary of the events is below.

Procedures	Pre-Op	Surgery	Discharge	6 Months +/- 4 weeks	12 Months + 8 weeks	24 Months + 8 weeks
Informed Consent & Eligibility Review	X					
Preoperative History & Physical	X					
Clinical & Neurological Evaluation	X		X	X	X	X
Surgery		X				
Discharge			X			
PI Radiological Assessment				X	X	X
Disposition						X
Routine X-rays (4 views)	X			X	X	X
Thin-slice (<math>\leq</math> 1.25 mm) lumbar CT scan w/o contrast with coronal and sagittal mpr					X	X*
Participant Forms (4)	X			X	X	X

\* = If clinically indicated, participants will complete a lumbar CT scan without contrast (e.g., PI determines there is a clinical need or the independent radiologist observed no posterolateral bridging bone in the 12 month CT).

### ***B. Data Collection***

Copies of all forms will be provided and will include all relevant information from the protocol and are included as supplemental documents. Clinical data (i.e., no prior written or electronic record of data) may be directly reported on case report forms (CRFs) by the PI (or designee) or participant and considered to be source data.

There will be CRFs for the pre-operative, intra-operative, discharge and post-operative visits.

- The PI (or designee) will complete the following CRFs.
  - Pre-operative eligibility: CRF 1P
  - Pre-operative medical history: CRF 2Q

P CRF 1 - Pre-operative eligibility

Q CRF 2 - Pre-operative medical history

- Pre-operative clinical and neurological evaluation and diagnosis: CRF 3R
- Operative Data: CRF 6S
- Discharge Data: CRF 7T
- Post-operative clinical and neurological evaluation: CRF 8U
- Post-operative radiological evaluation: CRF 9V
- Participant disposition: CRF 12W
- Complications/adverse events: Complications/Adverse Events FormX
  
- The Participant will complete the following self administered questionnaires (completion of these CRFs should be supervised but not influenced):
  - Pre-operative demographics & work status: CRF 4Y
  - Pre-operative VAS for back and leg pain and medication useZ: CRF 5AA
  - Post-operative work status: CRF 10BB
  - Post-operative VAS for back and leg pain, medication use and satisfaction with procedure: CRF 11CC
  - ODI for lower back pain: CRF ODIDD, EE, FF
  - RAND 36-item health survey: CRF 36-Item HSGG, HH

### ***C. Surgical Technique***

This is a routine bilateral, instrumented PLF surgery where nanOss Bioactive 3D will be hydrated with autologous BMA and placed bilaterally on a bed of local autograft bone spanning the transverse processes of the treated segment(s). The procedure should generate enough local autograft bone for use in the posterolateral spine and the interbody space (if applicable).

R CRF 3 - Pre-operative clinical & neurological evaluation and diagnosis

S CRF 6 - Surgery Information

T CRF 7 - Discharge Information

U CRF 8 - Post-Operative Clinical & Neurological Evaluation

V CRF 9 - Post-Operative PI Radiological Assessment

W CRF 12 - Participant Disposition

X CRF Complications & Adverse Events

Y CRF 4 - Pre-Operative Demographics & Work Status

Z Wewers, M. E. and Lowe, N. K. (1990). A critical review of visual analogue scales in the measurement of clinical phenomena. *Research in Nursing & Health*, 13: 227-236.

AA CRF 5 - Pre-Operative Pain & Medication Use

BB CRF 10 - Post-Operative Work Status

CC CRF 11 - Post-Operative Pain, Medication Use & Satisfaction

EE [name] et al (2006). MOS Short Form 36 and Oswestry Disability Index outcomes in lumbar fusion: a multicenter experience. *The Spine Journal*, 6: 21-26.

FF CRF ODI

GG Hays, RD (1994). *Medical Outcomes Study (MOS) Measures of Patient Adherence*. Retrieved April 19, 2004, from the RAND Corporation web site: <http://www.rand.org/health/surveys/MOS.adherence.measures.pdf>.

HH CRF 36-Item HS

If an interbody fusion is performed, only a PLIF or TLIF with PEEK IBF devices (with autograft) may be performed. Pioneer hardware and instrumentation (e.g., Streamline TL pedicle screw system, T-Plus IBF device, Bullet-Tip IBF device) should be used on Study participants. Upon prior approval by the Sponsor, a posterior, thoracolumbar, titanium pedicle screw system cleared for use at the segment treated must be used on participants to obtain rigid stabilization.

It is suggested that graft be placed in the posterolateral spine after irrigation has taken place to minimize any loss of graft material.

The recommended total graft mass in the posterolateral spine is 20 cc per treated segment.

$$10\text{cc of graft mass per side} = 5\text{cc autograft bone} + 5\text{cc nanOss Bioactive 3D}$$

### 1. BMA

Autologous BMA will be used to hydrate the nanOss Bioactive 3D strip.

- 10 cc of BMA should be harvested for each treated segment.
- The BMA may be harvested from the pedicles of the lumbar vertebrae (following initial preparation of the pedicle screw path) or from the posterior iliac crest using conventional techniques.
- The sites of aspiration will be recorded.
- The amount of BMA used to hydrate the nanOss Bioactive 3D strip will be measured prior to use and recorded.

The volume of autologous BMA used to rehydrate nanOss Bioactive 3D should be appropriate for the selected size (see table below). Soak nanOss Bioactive 3D in the BMA using manual compression for at least 5 minutes to ensure complete uptake of the BMA. The length of hydration time will be recorded.

nanOss Bioactive 3D strip size	Minimum Amount of BMA
5cc: 25x50x4 mm	4 mL
10cc: 25x100x4 mm	8 mL
10cc: 25x50x8 mm	8 mL
20cc: 25x100x8 mm	16 mL

### 2. Local Autograft Bone

Local autograft bone will be used to make an autograft bed placed directly on the decorticated site(s) and spanning the transverse-processes bilaterally.

- 10 cc of autograft bone is recommended for each treated segment (5cc per side).
  - No less than 5cc of autograft bone may be used in the posterolateral spine for each treated segment (2.5cc/side).
  - Equivalent amounts of autograft bone placed bilaterally.

- The autograft bone may be harvested locally, the soft tissue cleaned from the bone and then morselized using conventional techniques.
- The amount of autograft bone placed bilaterally in the posterolateral spine will be measured prior to use and recorded.
- The sites and volume of autograft collection will be recorded.
- It will be documented how the autograft bone was morselized.

### **3. nanOss Bioactive 3D**

nanOss Bioactive 3D will be placed on top of the bed of autograft bone spanning the transverse-processes of the treated segment bilaterally.

- 10 cc of nanOss Bioactive 3D should be used for each segment treated (5cc/side).
- The amount of nanOss Bioactive 3D placed on each side of the posterolateral spine will be recorded.
- Equivalent amounts of nanOss Bioactive 3D placed bilaterally (see description and images below).
  - Single segment procedure options following rehydration:
    - A 5cc (25x50x4 mm) nanOss Bioactive 3D strip may be applied to each side of the treated segment (2 strips).
    - A 10cc (25x50x8 mm) nanOss Bioactive 3D strip may be cut in half lengthwise and applied bilaterally at the treated segment (1 strip).
    - A 10cc (25x100x4 mm) nanOss Bioactive 3D strip may be cut in half and applied bilaterally at the treated segment (1 strip).
  - Two segment procedure options following rehydration:
    - A 5cc (25x50x4 mm) nanOss Bioactive 3D strip may be applied to each side of each segment (4 strips).
    - A 10cc (25x50x8 mm) nanOss Bioactive 3D strip may be cut in half lengthwise and applied bilaterally, spanning both segments on each side (2 strips).
    - A 10cc (25x100x4 mm) nanOss Bioactive 3D strip may be applied to each side spanning both segments on each side (2 strips).
    - A 20cc (25x100x8 mm) nanOss Bioactive 3D strip may be cut in half lengthwise and applied bilaterally, spanning both segments on each side (1 strip).

### **D. Radiological Studies**

As part of routine care, participants have a series of pre-operative and post-operative radiographic studies performed. Pre-operative DEXA scans should only be performed as part of routine care for at risk patients.

## 1. LAT, FLX & EXT X-Ray Guidelines

The x-ray system should be set up according to standard protocol for lateral lumbar spine x-ray.

- Include the calibration marker around the subject's waist and in the field of view in all lateral x-rays.

## 2. AP X-Ray Guidelines

The x-ray system should be set up according to standard protocol for an AP lumbar spine x-ray.

- Do not include the calibration marker in this x-ray.

## 3. Lumbar CT Scan (without contrast) Guidelines

The CT manufacturer's spine imaging protocols should be followed as long as it specifies acquisition of original axial slices that are  $\leq$  1.25 mm thick.

- Sagittal and coronal reformatting is required. See the radiograph acquisition protocol for specific guidelines.
- The entire fusion mass at the treated segment(s) must be included.

## E. Radiological Study Transmission

The following radiographic studies are required to be transmitted to the independent radiological reviewer as shown below:

- Pre-operative: Neutral AP/Lateral & Flexion/Extension x-rays.
  - Images should be within approximately 6 months.
- 6 Months Post-operative: Neutral AP/Lateral & Flexion/Extension x-rays.
- 12 Months Post-operative: Neutral AP/Lateral & Flexion/Extension x-rays & a thin-slice lumbar CT scan (without contrast) with sagittal and coronal reformatting.
- 24 Months Post-operative: Neutral AP/Lateral & Flexion/Extension x-rays & a thin-slice lumbar CT scan (without contrast) with sagittal and coronal reformatting, as applicable.

X-rays transmitted to the independent radiological reviewer should be in a format that permits electronic transmission. If this is not permitted at the site CDs/DVDs may be used. An Image Transmittal Form must be used with any x-ray transmission to the Independent radiologist.II In order to accurately measure the x-rays, the following apply to post-operative plain x-rays:

- A scale should be placed on the plain x-rays for accurate measurements.
- The Right or Left side must be clearly indicated.
- The original, unformatted, thin-slice CT images must be sent to MMI along with all available orthogonal reformations.

---

II MMI Image Transmission Form (ITF)

#### ***F. PI Clinical & Neurological Assessment***

As part of their routine care, participants will have a pre-operative, discharge and post-operative clinical & neurological assessments performed. The following information will be recorded:

##### **Muscle Strength**

Muscle strength for the right and left sides will be tested in the:

- Hip Flexors and Extensors
- Knee Flexors and Extensors
- Foot/Toe Dorsi-Flexors
- Foot/Toe Plantar-Flexors

Scoring will be recorded using the following scale:

0. Absent (total paralysis)
1. Trace (palpable or visible contraction)
2. Poor (active movement, gravity eliminated)
3. Fair (active movement, against gravity)
4. Good (active movement, against resistance)
5. Normal
6. Not-Testable

##### **Sensory Deficit**

Sensory deficit will be measured by conducting a pinprick test for pain, a temperature test with a cold object and a touch test using a cotton ball or something similar. These tests indicate the participant's ability to sense an external source. Scoring will be recorded using the following scale:

- None - if the tests are negative, the PI will indicate that there are no deficits detected on any dermatone.
- If the participant cannot sense any of the above items, then the test is positive. If any of the tests are positive, the physician will determine which dermatome (L1 – S1) is affected and on which side it occurred (Right or Left).

##### **Reflexes**

Reflexes will be graded for the Right and Left Patellar and Achilles. Scoring will be recorded using the following scale:

0. Absent/Trace
1. Decreased
2. Normal
3. Hyperactive

### Straight Leg Raise

The Straight Leg Raise is where the participant lies supine on the examination table. The physician will lift the participant's leg upward supporting the foot and keeping the knee straight. The extent to which the leg can be raised without discomfort varies but normally the angle between the table and the leg measures approximately 70-80 degrees. Scoring will be recorded using the following scale:

1. If there is no pain, then the test is negative.
2. If the test is painful, the physician must determine whether the pathology is due to the sciatic nerve or to the participant's tight hamstrings. If the pain is due to the sciatic nerve, then the test is positive.

### ***G. PI Radiological Assessment***

Each PI will review the x-rays for any instances of heterotopic bone formation, hardware condition and any complications or adverse events. The PI will also assess the treated segment(s) according to the Lenke's classification of posterolateral fusion successJJ and record the results on the post-operative radiological assessment form according to the following criteria:

- Grade A - Definitely solid with bilateral trabeculated stout fusion masses present.
- Grade B - Possibly solid with a unilateral large fusion mass and a contralateral small fusion mass.
- Grade C - Probably not solid with a small fusion mass bilaterally.
- Grade D - Definitely not solid with bone graft resorption or obvious pseudoarthrosis bilaterally.

---

## XIV. COMPLICATIONS AND ADVERSE EVENTS

Safety assessment involves assessment of the complications, including subsequent surgical interventions and pain and neurological complication information. Pain, neurological and function symptoms should be considered complications when a patient's complaint for any of these symptoms results in an unscheduled visit or when a patient presents with new or worsening pain, neurological, and/or function symptoms as compared to the previous visit.

All non-serious operative and post-operative complications, whether or not they are related to the device, including both observed or volunteered problems, complaints, symptoms, physical signs, or diseases which occur during participation in the Study that were not present at the baseline evaluation, or were present at baseline but have worsened, are to be recorded by the PI and reported to the Sponsor.

- These should be reported to the Sponsor **no later than ten working days after the PI learns of the event.**
- This should be reported on the Complication/Adverse Event CRF.

Any serious and unanticipated serious adverse device events that have at least a possible relationship to nanOss Bioactive 3D are to be recorded on the Complication/Adverse Event CRF and reported to the Sponsor.

- These should be reported to the Sponsor **within 24 hours** of the PI becoming aware of the event via fax or email or telephone.
- The Sponsor will immediately conduct an evaluation of the events.

The Sponsor will ensure that the event is documented by the PI and reported to the appropriate authorities as required. The Sponsor has internal advisory boards composed of physicians that are available for questions and review of such events.

- A serious adverse event (SAE) is an anticipated AE that falls into one of the following categories: (a) death, (b) life-threatening adverse experience, (c) inpatient hospitalization or prolongation of hospitalization, (d) persistent or significant disability/incapacity, (e) congenital anomaly/birth defect, (f) important medical event that may jeopardize the participant and may require medical intervention to prevent an outcome listed in a-e above, or (g) any AE associated with the use of nanOss Bioactive 3D, the specificity or severity of which is not consistent with the risk information provided.
- An unanticipated serious adverse device effect (USADE) is an unanticipated serious adverse effect on health or safety or any life-threatening problem or death caused by, or associated with, nanOss Bioactive 3D, if that effect, problem, or death was not previously identified in nature, severity, or degree of incidence in the protocol, or any other unanticipated serious problem associated with nanOss Bioactive 3D that relates to the rights, safety, or welfare of participants.

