***B. Risks Associated with nanOss Bioactive 3D***

The primary risk associated with nanOss Bioactive 3D is the lack of a solid fusion. There may be other risks that are not currently known. Risks associated with bone void fillers include:

- Hematoma
- Site drainage
- Bone fracture
- Infection
- Fracture or extrusion of the bone void filler
- Deformity of the bone at the site
- Incomplete or lack of osseous bone ingrowth
- Continued pain
- Allergic reaction - nanoss Bioactive 3D contains a porcine (pig) collagen product which is sterilized as part of the manufacturing process
- Revision surgery

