### ***B. Secondary Endpoints***

An assessment of secondary endpoints will include an analysis of the following to determine trends in the data;

1. Assessment of fusion 6 and 24 months postoperatively.
2. Pain score improvement using the VAS.
3. Physical disability score improvement using the ODI.
4. Physical-functioning improvement using the 36-Item HS.
5. Satisfaction with procedure.
6. No serious adverse event classified as related to nanOss Bioactive 3D or no device failure or subsequent intervention, excluding the removal of fixation after a solid fusion occurred.

The following additional data will be presented:

- The sample size and percentage of successfully fused segments 6 and 24 months postoperatively.
- Sample sizes and percentages of successfully fused segments for different groups based on smoking status, age, sex, BMI, the number of segments treated and whether or not an IBF device was used 24 months postoperatively.
- Demographic information will be presented as sample sizes and percentages.
- Satisfaction with procedure will be presented as sample sizes and percentages for each visit.

- Pain, physical disability and physical-functioning scores will be presented as sample sizes, means, standard deviations and ranges for each visit. The post-operative results will be compared to baseline levels.
- The proportion of clinical complications, reoperations, revisions, as well as unexpected adverse events will be calculated.

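### The SAE definition mixes expectedness with seriousness and contradicts itself, so a mild unexpected nanOss-associated event can be classed either way

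*Combined protocol and SAP*

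**What the plan says.** Section XIV (Complications and Adverse Events) opens its definition thus: "A serious adverse event (SAE) is an anticipated AE that falls into one of the following categories". Categories (a) to (e) are outcomes, from death to congenital anomaly. Category (f) has a threshold of medical importance: "important medical event that may jeopardize the participant and may require medical intervention to prevent an outcome listed in a-e above". Category (g) is of another kind: "any AE associated with the use of nanOss Bioactive 3D, the specificity or severity of which is not consistent with the risk information provided".

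The next definition in the section is also about unexpected device events, but it requires seriousness: "An unanticipated serious adverse device effect (USADE) is an unanticipated serious adverse effect on health or safety or any life-threatening problem or death". Its test of expectedness is "if that effect, problem, or death was not previously identified in nature, severity, or degree of incidence in the protocol".

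Section XIV uses the serious/non-serious split for reporting. Non-serious complications, related or not, go to the Sponsor within ten working days. Serious events with at least a possible relationship to nanOss Bioactive 3D go within 24 hours, and the Sponsor evaluates them at once.

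Section XIX.B lists safety as item 6 of the secondary endpoints: "No serious adverse event classified as related to nanOss Bioactive 3D or no device failure or subsequent intervention", with an exception for removal of fixation after solid fusion. The same section separately promises a proportion of unexpected adverse events.

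**The concern.** Seriousness and expectedness are different attributes of an event. Seriousness describes the outcome; expectedness describes whether the event fits the known risk profile. Category (g) lets the second stand in for the first. The word 'anticipated' in the lead-in does the reverse, making expectedness a condition of being an SAE at all. One sentence therefore pulls in opposite directions on the same event.

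Section XIV holds the only SAE definition in the documents, so item 6 has no other to rely on. Two things are at stake. The first is consistent classification across up to 10 sites (XII.B), which decides the reporting route. The second is the meaning of the related-SAE part of item 6: a count that may or may not include mild events is hard to interpret and hard to set beside published results. X.B says the study's results will be compared with the literature, and it includes complications and adverse events among the information to be gathered.

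**Working it through.** There is no stated figure to reproduce: the documents give no safety rate, performance goal or sample-size calculation for this endpoint. The check is a reading of the definitions, followed by the weight of one participant.

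**Step 1. Run three kinds of nanOss-associated event through the text.**

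| Event | Lead-in ('anticipated') | Category met | USADE? | Result |
|---|---|---|---|---|
| Mild, type not in the risk information | Fails on a literal reading | (g) | No, not serious | SAE if (g) governs; non-serious if the lead-in governs |
| Mild, listed type, but severity judged not to fit the risk information | Arguable: the type is anticipated, the severity is not | (g) | No, not serious | SAE under (g), with no outcome criterion met |
| Serious, type not in the risk information | Fails on a literal reading | (g), plus whichever of (a) to (f) applies | Yes | USADE; literally not an SAE |

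The first row is the contradiction. The second shows that (g) is not emptied by the lead-in, because it reaches severity as well as type. The third shows why the lead-in cannot be left alone: item 6 names SAEs and does not name USADEs.

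**Step 2. Follow the consequences for a mild event.** If it is called serious, it takes the 24-hour route and, if classified as related, can enter item 6. If it is called non-serious, it takes the ten-working-day route and stays out of the SAE part of item 6. No rule says which reading applies.

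**Step 3. Size of one classification.** Inputs: 50 participants expected (XII.C); at most 60 (XII.B).

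- Weight of one participant = 1/N.
- N = 50: 1/50 = 0.020, or 2.0 percentage points.
- N = 60: 1/60 = 0.0167, or 1.7 percentage points.

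The documents give no rate of mild, unexpected, nanOss-associated events. As an assumption, 0 to 5 such participants of 50 would move the related-SAE part by 0/50 = 0 to 5/50 = 10 points; at 60, 0 to 5/60 = 8.3 points.

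**The case against.** A reader might infer that (g) makes every minor unlisted complaint a related SAE and so inflates the reported rate several-fold. The documents do not support that, for these reasons.

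- **The lead-in points the other way.** An SAE must be anticipated and must also fall into a category. An event outside the risk information is hard to call anticipated. This stands against any claim that such events are certainly counted. It does not rescue the definition, because it leaves (g) at odds with its own opening words.
- **Association is not classification.** Item 6 needs an event classified as related; (g) speaks of association. The two are close, but no rule links them, and the documents do not say who classifies relatedness. So such an event can enter item 6 but need not.
- **The logic of item 6 is itself unclear.** Its parts are joined by 'or', so on a literal reading a related SAE alone need not fail the endpoint. The sizes above therefore apply to the SAE part, not to item 6 as a whole.
- **Few events may fall outside the risk information.** XVII.B introduces its list with "Risks associated with bone void fillers include" and gives ten entries, among them hematoma, site drainage, infection and continued pain. XVII.A adds 34 surgical risks (9 common, 25 less frequent). Product labeling and instructions for use are supplements not seen here. XVII.B grades no severities, but it cannot be said that the severity test in (g) is unworkable without those supplements.
- **Any multiple of a true rate is assumed.** VI.E says there are no clinical data for this product in the posterolateral spine, so there is no base rate from which to compute an inflation factor. XIX.B does not list a stand-alone related-SAE proportion, and X.B does not name SAE rates as a comparison.
- **Early notice of unexpected device-associated events is a reasonable sponsor choice.** That is so, but it does not require calling them serious.

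What survives is the missing threshold in (g), its conflict with the lead-in, and the resulting doubt over how one event is classed.

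**Conclusion.** The point holds as a defect in a stated rule, not as a demonstrated bias. The definition uses unexpectedness as a route into seriousness in (g) and as a bar to it in the lead-in. A mild nanOss-associated event that does not fit the risk information can be classed either way. This affects the reporting route and the related-SAE part of item 6, by 2.0 points per participant at 50 or 1.7 at 60. The number of such participants is unknown and may be zero; the 0 to 10 point range at 50 rests on an assumed 0 to 5 participants.

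The direction of any error is not fixed. Following (g) would add mild events. Following the lead-in would leave serious unexpected device events outside the term that item 6 uses. Item 6 is one of the secondary endpoints analysed for trends, without a test or threshold, and the primary fusion endpoint is untouched. The correction should be made because it is cheap and removes an ambiguity in the safety reporting, not because the study's main conclusion depends on it.

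**What to change.** Make these changes together:

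1. In XIV, define an SAE by categories (a) to (f) regardless of expectedness: delete 'anticipated' from the lead-in and remove (g) from the list. Deleting (g) alone would leave serious unexpected device events only under USADE. Deleting 'anticipated' alone would make (g) fully operative.
2. Turn the content of (g) into an 'unexpected' flag on the Complication/Adverse Event CRF, completed for every event, serious or not. The flag would feed both the USADE definition and the unexpected-event proportion already promised in XIX.B.
3. In XIX.B, state that item 6 counts related events meeting (a) to (f), including those that are also USADEs.

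The Sponsor can keep its 24-hour report for flagged related events without labelling them SAEs, so no early notice is lost. The cost is a few lines of protocol wording and one check box on an existing form. The one downside is presentational: unexpected non-serious events move from the SAE table to the unexpected-event table.
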